### **Shift Tables**

Shift tables will be provided for each hematology, clinical chemistry parameter. Shifts from Baseline to the following endpoints will be considered: post-Baseline value and final value. This analysis will be performed only for category of "low or normal" at Baseline which shift to 'high' and category of "high or normal" at Baseline which shift to category of 'low.' If there are multiple post-baseline measurements on the same day, last value will be used.

### **Potentially Clinically Significant Laboratory Values**

Frequencies and percentages of subjects with post Baseline lab values met the following criteria in [Table 4](#) and [Table 5](#) will be summarized. Of note, a post baseline value must be more extreme than the baseline value to be considered a potentially clinically important finding.

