3. DESCRIPTION OF DESIGN AND TRIAL POPULATION

3.1 OVERALL TRIAL DESIGN AND PLAN

This open label extension trial (OLE), investigates the additional safety and efficacy of the 90 mg dose of BI 655066. Approximately 100 patients who meet the entry criteria are planned for inclusion in this trial, rolling over from the preceding 1311.2 trial. The treatment will be open label.

The treatment period will be approximately four years of administration starting with first administration of BI 655066 in either trial 1311.2 or 1311.13, followed by a 12 week follow up period. After 01-May-2018 and approval of this protocol amendment in each respective country, the next study visit will be the Extended EOS visit and therewith the last visit in this study. Patients who have completed the study without early treatment discontinuation will be offered to roll over to M15-997 open label extension (OLE) trial if they fulfill the in- and exclusion criteria for the M15-997 trial. Refer to [section 6.2.3](#).

Patients rolling over from the preceding trial 1311.2 will have to complete the treatment period in that trial, or complete the entire trial including the follow up period, reaching end of study. If, during the follow up period of the preceding trial (at any visit from week 24 and onwards in trial 1311.2) loss of response is detected, the patient can roll over in this extension trial. For this, loss of response is defined as $< \text{PASI}_{50}$.

Extended visit 1 of this trial should preferably be performed as a combined visit the same day as End of Study visit of 1311.2, or within an interim period of maximum 6 weeks thereafter.

1311.2

[figure not shown]
[figure not shown]

Figure 3.1:1 Guideline for roll over of patients from 1311.2 to OLE study 1311.13

After the approval of this protocol amendment in each respective country, all patients will follow [Flow Chart](#) (Extended Dosing Period) and receive 90mg BI 655066 subcutaneously at their Extended visit 1 (EV1). From EV1 onwards, BI655066 will be administered subcutaneously every 12 weeks during the trial. At EV2, if there is a lack of response, defined as <PASI90, the dose should be increased to 180mg for the remainder of the trial (see Fig 3.1.2).

For ongoing patients under the previous protocol amendment (Pre-Extended Dosing Period, [see Fig 3.1.3](#)), EV1 should be conducted at the following time points:

1. For ongoing patients with ≥ 12 weeks since the EOT visit: Conduct EV1 as soon as possible

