## **11.3 Analysis of Laboratory Data**

Listing and descriptive statistics of laboratory values over time and extreme abnormal value on treatment will be provided. Baseline is the last non-missing values on or before the date of the first dose of risankizumab either in Study 1311.2 or this study. Extreme abnormal value on treatment is the on treatment laboratory value which is most significantly away from the reference range. Frequency of subjects with transitions relative to reference range and listing of subjects with significant abnormal laboratory values will be presented as well.

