**Table 4. Criteria for Potentially Clinically Important Chemistry Values**

Chemistry Variables	Units	Definition of Potentially Clinically Important Current (Version 4) NCI CTCAE Grade 3 or greater	
		Very Low	Very High
Bilirubin Total	mcmol/L		$> 3.0 \times \text{ULN}$
AST (GOT)	U/L		$> 5.0 \times \text{ULN}$
ALT (GPT)	U/L		$> 5.0 \times \text{ULN}$
Glucose	mmol/L	< 2.2	> 13.9
Triglycerides	mmol/L		> 5.7
Creatinine	mcmol/L		$> 3.0 \times \text{ULN}$
Sodium	mmol/L	< 130	> 155
Potassium	mmol/L	< 3.0	> 6.0
Calcium	mmol/L	< 1.75	> 3.1
CK	U/L		$> 5.0 \times \text{ULN}$
Cholesterol, total	mmol/L		> 10.34
ALP			$> 5.0 \times \text{ULN}$

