**Table 5. Criteria for Potentially Clinically Important Hematology Values**

Hematology Variables	Units	Definition of Potentially Clinically Important Current (Version 4) Grade 3 or greater	
		Very Low	
Hemoglobin	g/dL		< 8.0
Platelets count	$10^9/\text{L}$		< 50.0
White Blood Cells	$10^9/\text{L}$		< 2.0
Neutrophils	$10^9/\text{L}$		< 1.0
Lymphocytes	$10^9/\text{L}$		< 0.5

A separate listing will be provided that presents all of the subjects and values that are NCI CTCAE toxicity grade 3 or above. For each of these subjects, the whole course of the respective parameter will be listed.

If there are multiple measurements on the same day, the worst value will be used.

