**Table 6. Criteria for Potentially Clinically Significant Vital Sign Findings**

Vital Sign	Category	Criteria for Potential Clinically Significant Vital Signs
Systolic Blood Pressure	Low Value	$\leq 90$ mmHg and decrease $\geq 20$ mmHg from Baseline
	High Value	$\geq 160$ mmHg and increase $\geq 20$ mmHg from Baseline
Diastolic Blood Pressure	Low Value	$\leq 50$ mmHg and decrease $\geq 15$ mmHg from Baseline
	High Value	$\geq 105$ mmHg and increase $\geq 15$ mmHg from Baseline
Pulse	Low Value	$\leq 50$ bpm and decrease $\geq 15$ bpm from Baseline
	High Value	$\geq 120$ bpm and increase $\geq 15$ bpm from Baseline

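### SAP 11.3.2 mixes laboratory abnormalities present before treatment with new ones: a patient persistently at Grade 3 or above at baseline can enter the counts for Tables 4 and 5 without any worsening.

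*SAP*

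**What the plan says.** The rule is in SAP 11.3.2, under Potentially Clinically Significant Laboratory Values. Frequencies and percentages of subjects with post-baseline values meeting Tables 4 and 5 are to be summarised, and "a post baseline value must be more extreme than the baseline value to be considered a potentially clinically important finding". Table 4 heads its cut-offs "Definition of Potentially Clinically Important Current (Version 4) NCI CTCAE Grade 3 or greater", and Table 5 gives the matching haematology limits. The same-day rule after Table 5 is "If there are multiple measurements on the same day, the worst value will be used".

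The comparator is one reading. SAP 11.3 states: "Baseline is the last non-missing values on or before the date of the first dose of risankizumab either in Study 1311.2 or this study".

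Three other SAP provisions treat baseline differently:

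- **Vital signs (Table 6).** The same more-extreme condition applies, but each criterion also demands a minimum change. For high systolic pressure this is "increase $\geq 20$ mmHg from Baseline".
- **Shift tables.** These are restricted by baseline category: "This analysis will be performed only for category of 'low or normal' at Baseline which shift to 'high". The mirror-image restriction applies to shifts to low.
- **Listing after Table 5.** A separate listing "presents all of the subjects and values that are NCI CTCAE toxicity grade 3 or above", with the whole course of the parameter for each such subject.

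**The concern.** If a patient's baseline is already at Grade 3 or above, any more extreme value is automatically Grade 3 or above as well. The two-part rule then reduces to whether any later reading lies beyond one earlier reading. For example, triglycerides of 5.8 mmol/L at baseline and 5.9 later would count against the 5.7 cut-off. The patient gets a fresh opportunity at every laboratory visit.

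What is at stake is how the summary percentages are read. Protocol 2.2 makes safety the primary objective. There is no control arm and about 100 patients are planned, so one or two long-standing abnormalities could be a visible share of a Grade 3+ row. The summary table alone would not separate them from abnormalities that arose on treatment.

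**Working it through.** The plan gives no expected count, prevalence or operating characteristic for this rule, so there is no figure of its own to reproduce.

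**Inputs from the documents**

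- Rule: post-baseline value at Grade 3+ and more extreme than baseline (SAP 11.3.2).
- Baseline: one reading, the last on or before first risankizumab (SAP 6.0 and 11.3).
- Interval: "From EV1 onwards, BI655066 will be administered subcutaneously every 12 weeks during the trial" (Protocol 3.1). The Flow Chart marks safety laboratory tests at each extended visit, so EV2 to EV18 (weeks 12 to 204) give up to k = 17 later samples.
- Protocol 3.1 also closes the study after 01-May-2018, so many patients will have fewer. I use k = 4 (one year), 12 and 17.
- Planned size: about 100 patients (SAP 4.2).

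**Assumptions (not in the documents)**

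- Within-patient correlation (ICC) of 0.5 to 0.9, normally distributed readings, and no true change.
- Cut-off at the 98th or 99th percentile of the population.
- 0 to 2 patients per 100 already meeting a given criterion at baseline.

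**Step 1. Persistently abnormal, stable patient.** If the baseline and the k later readings are exchangeable without ties, each of the k+1 readings is equally likely to be the most extreme. The patient escapes only if the baseline is the most extreme:

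P(counted) = 1 − 1/(k+1) = k/(k+1)

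- k = 4: 4/5 = 80%
- k = 12: 12/13 = 92%
- k = 17: 17/18 = 94%

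**Step 2. Allowing for regression to the mean.** Let b be the baseline, standard normal and conditioned to exceed the cut-off. The patient's mean m given b is normal with mean ICC × b and variance ICC(1 − ICC). Later readings scatter around m with variance 1 − ICC. Then

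P(counted) = 1 − E[ Φ( (b − m)/√(1 − ICC) )^k ]

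Numerical integration gives:

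| Cut-off | ICC | k = 4 | k = 12 | k = 17 |
|---|---|---|---|---|
| 98th percentile | 0.5 | 25% | 46% | 53% |
| 98th percentile | 0.7 | 39% | 61% | 68% |
| 98th percentile | 0.9 | 59% | 78% | 83% |
| 99th percentile | 0.5 | 20% | 39% | 46% |
| 99th percentile | 0.7 | 35% | 56% | 63% |
| 99th percentile | 0.9 | 56% | 76% | 81% |

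The range is 20-59% at 4 samples and 39-78% at 12. Low correlation represents the isolated high baseline, which usually is not exceeded when few samples follow. High correlation approaches the persistent case of Step 1.

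**Step 3. Expected count per row.** The number of patients must match the percentile used. A 98th-percentile cut-off implies 2 per 100, and a 99th-percentile cut-off implies 1 per 100. At 12 samples:

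- 0 patients: 0
- 1 patient (99th percentile): at most 1 × 0.76 = 0.8
- 2 patients (98th percentile): at most 2 × 0.78 = 1.6

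If both of two such patients were persistently abnormal and had all 17 samples, Step 1 would give 2 × 17/18 = 1.9.

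**Step 4. Everyone else.** For a patient below Grade 3 at baseline, any Grade 3+ value is already more extreme than baseline. The condition does nothing for these patients, and their counts do not change under the fix below.

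**The case against.** **A defence of the plan has several good points.**

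- The more-extreme condition can only remove subjects relative to a plain Grade 3+ count; it never adds any. This stands. The criticism is that the condition removes few of the persistent cases, not that it inflates a plain count.
- The whole-course listing shows whether a counted subject was already beyond the cut-off. This also stands, and it is the main reason the point is minor. The listing does not, however, alter the frequencies and percentages in the summary table.
- Protocol 3.3.3, exclusion 8, removes patients with clinically significant laboratory abnormalities on the last available results of trial 1311.2. This limits the problem but does not close it. The exclusion rests on investigator judgement, not on a grade. For patients first given risankizumab in 1311.2 (Protocol 2.3 puts 75% of that trial's patients on the drug), the safety baseline predates the screen.
- The analysis is descriptive (SAP 6.0), and no test or decision hangs on these rows. Leaning towards inclusion in a safety table is defensible.
- Table 6 is not a perfect model. A systolic pressure of 165 mmHg at baseline and 185 later meets its criterion, so it too admits patients who were already abnormal.

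**Stronger readings that the documents do not support.** A reader might infer that patients at Grade 3+ before treatment will mostly be counted. At one year the calculated chance is as low as 20%, and it stays below one half unless the correlation is high. A reader might also infer that particular tests will be dominated by such cases, or that pre-existing cases cannot be identified without a control arm. The documents give no baseline frequency for any test, and the listing does identify the patients.

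**Conclusion.** The point holds in a limited form and is minor. The rule is as described. For a patient persistently at Grade 3+ before risankizumab it is a weak filter, with an 80% to 94% chance of being counted without change over 4 to 17 samples. When regression to the mean is allowed for, the chance is about 20-59% at 4 samples and 39-78% at 12. The documents do not give the number of patients exposed to this, and it may be zero. At 0 to 2 per 100, about 0 to 1.6 subjects per row would be counted without worsening.

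The k/(k+1) result needs only exchangeable readings without ties. The other figures rest on the assumed normality, correlation, cut-off percentile and prevalence. The rule merits a change because the change is nearly free and the trial is uncontrolled with safety as its primary objective. The planned analysis is not invalid as it stands.

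**What to change.** In SAP 11.3.2, for each criterion in Tables 4 and 5, report two things:

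1. New-onset subjects: those whose baseline did not meet the criterion and who met it afterwards. The denominator is the subjects who did not meet it at baseline.
2. In a separate row, subjects who already met the criterion at baseline, with the number whose CTCAE grade then rose (for example from Grade 3 to Grade 4).

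Keep the Grade 3+ whole-course listing for all subjects. The separate row matters because a new-onset rule alone would drop a rise from Grade 3 to Grade 4, whereas a rule based on any rise in grade would keep it. Reporting both avoids having to choose.

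The cost is a sentence or two in the SAP and one extra row per parameter; baseline grade comes from the scale the SAP already applies. The downside is that worsening within the same grade would appear only in the listing.

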**Table 4. Criteria for Potentially Clinically Important Chemistry Values**

Chemistry Variables	Units	Definition of Potentially Clinically Important Current (Version 4) NCI CTCAE Grade 3 or greater	
		Very Low	Very High
Bilirubin Total	mcmol/L		$> 3.0 \times \text{ULN}$
AST (GOT)	U/L		$> 5.0 \times \text{ULN}$
ALT (GPT)	U/L		$> 5.0 \times \text{ULN}$
Glucose	mmol/L	< 2.2	> 13.9
Triglycerides	mmol/L		> 5.7
Creatinine	mcmol/L		$> 3.0 \times \text{ULN}$
Sodium	mmol/L	< 130	> 155
Potassium	mmol/L	< 3.0	> 6.0
Calcium	mmol/L	< 1.75	> 3.1
CK	U/L		$> 5.0 \times \text{ULN}$
Cholesterol, total	mmol/L		> 10.34
ALP			$> 5.0 \times \text{ULN}$

**Table 5. Criteria for Potentially Clinically Important Hematology Values**

Hematology Variables	Units	Definition of Potentially Clinically Important Current (Version 4) Grade 3 or greater	
		Very Low	
Hemoglobin	g/dL		< 8.0
Platelets count	$10^9/\text{L}$		< 50.0
White Blood Cells	$10^9/\text{L}$		< 2.0
Neutrophils	$10^9/\text{L}$		< 1.0
Lymphocytes	$10^9/\text{L}$		< 0.5

A separate listing will be provided that presents all of the subjects and values that are NCI CTCAE toxicity grade 3 or above. For each of these subjects, the whole course of the respective parameter will be listed.

If there are multiple measurements on the same day, the worst value will be used.

## **Liver Function Tests**

A listing of possible Hy's Law cases, defined as those who meet all of the following conditions will be provided:

- ALT  $> 3 \times$  ULN or AST  $> 3 \times$  ULN
- Associated with an increase in bilirubin  $\geq 2 \times$  ULN
- Alkaline phosphatase  $< 2 \times$  ULN

## **11.4 Analysis of Vital Signs and Weight**

### **11.4.1 Variables and Criteria Defining Abnormality**

The following vital sign parameters will be assessed: Systolic blood pressure [mmHg], Diastolic blood pressure [mmHg], Pulse [beats per minute], Respiratory rate [breaths per minute], Temperature [ $^{\circ}$ C], Weight [kg]. The following [Table 6](#) presents the Criteria for Potentially Clinically Significant Vital Sign Findings. Of note, a post baseline value must be more extreme than the baseline value to be considered a potentially clinically important finding.

**Table 6. Criteria for Potentially Clinically Significant Vital Sign Findings**

Vital Sign	Category	Criteria for Potential Clinically Significant Vital Signs
Systolic Blood Pressure	Low Value	$\leq 90$ mmHg and decrease $\geq 20$ mmHg from Baseline
	High Value	$\geq 160$ mmHg and increase $\geq 20$ mmHg from Baseline
Diastolic Blood Pressure	Low Value	$\leq 50$ mmHg and decrease $\geq 15$ mmHg from Baseline
	High Value	$\geq 105$ mmHg and increase $\geq 15$ mmHg from Baseline
Pulse	Low Value	$\leq 50$ bpm and decrease $\geq 15$ bpm from Baseline
	High Value	$\geq 120$ bpm and increase $\geq 15$ bpm from Baseline

**11.4.2 Statistical Methods**

Observed values at each scheduled visit in vital sign parameters will be summarized with the mean, standard deviation, median, minimum and maximum. If there are multiple post-baseline measurements on the same day, average value will be used.

For systolic blood pressure, diastolic blood pressure and pulse, a listing of all subjects with any vital sign value meeting criteria for potentially clinically important values will be provided. For each of these subjects, the whole course of the respective parameter will be listed. The number and percentage of subjects who have at least one value meeting criteria for potentially clinically important values will be provided for each vital sign parameter.

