7. "xT" is a targeted physical examination including assessment of vital sign measurements, and evaluation of organ systems associated with AE(s) symptoms or laboratory abnormalities.
8. Measured after 5 minutes of rest in the supine position. Measurements of vital signs should, if possible, always precede blood sampling.
 - a. Extended visit 1: Vital signs will be taken ~ 30 min pre-dose, 5 minutes, and 1 hour after the dose is administered
 - b. Following dosing visits: Vital signs will be taken ~ 30 min pre-dose, 5 minutes, and 1 hour after the dose is administered
 - c. Non-dosing visit (Extended EOS): Vital signs will be measured once per visit
9. ECG to be performed after 5 minutes of rest in the supine position, at every 24 weeks, starting from EV1 (EV1, EV3, EV5...). Should, if possible, be performed prior to blood sampling.
10. Not to be performed for patients who prematurely discontinue the treatment period.
11. All new AEs as well as unresolved AE from the preceding trial 1311.2 should be followed up within this study.
12. Only for patients with psoriatic arthritis.
13. For details of laboratory tests cf. [Section 5.2.3](#), [Table 5.2.3:1](#) and [5.2.3.2](#)
14. Patients must be fasting for at least 8 hours prior to collection of the safety laboratory samples.
15. Only applicable for women of childbearing potential.
16. In women of childbearing potential urine pregnancy test has to be performed before each administration of study drug.
17. Blood samples for protein biomarker, PK and ADA will be drawn ~ 30 min before the subcutaneous injection (PreD) at every 24 weeks, starting from EV1 (EV1, EV3, EV5...).
18. For patients who prematurely discontinue the follow up period before study end (for any reason), an early Extended EOS visit is required. This early Extended EOS visit will include the same procedures as the normal Extended EOS visit.
19. Patients will be asked to give consent to be contacted (or for their primary care physician to be contacted) by the study team to obtain vital status information preferably at the time of study entry
20. Only required at EV1 for patients who are having EV1 as their first 1311.13 visit
21. All efficacy assessments should be performed pre-dose (PreD)
22. To be repeated once per year until study end (EV1, EV5, EV10...)

Proprietary confidential information.

© 2018 Boehringer Ingelheim International GmbH or one or more of its affiliated companies. All rights reserved.

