4.1.4 Drug assignment and administration of doses for each patient

The study drug will be administered by the physician investigator or by authorised study personnel (e.g. study nurse). The study drug will be administered as a subcutaneous injection in the abdomen, thighs, gluteal regions, or upper arms. Injections being given in the same area should be at least 2 cm apart and should not be close to a vein. The injection site should avoid sites of psoriasis involvement as well as sites where the skin is tender, bruised, erythematous, or indurated, and should be alternated to other areas for subsequent doses.

Further information regarding technique of injection and injection materials (syringes, needles) will be provided in the ISF. For 180 mg doses, two syringes of 1 ml BI 655066, each of 90 mg, will be allocated and injected. Dilution of the study medication is not allowed and no dose modification, apart from the protocol specified doses, is permitted.

Administration of biologic agents involves the risk of local (injection site) or systemic hypersensitivity reactions. Therefore the patients should be closely monitored for signs and symptoms of hypersensitivity reactions for approximately 1 hour after the first dose administered, and 30 minutes following all other doses of study drug. Study personnel should observe the injection site for signs of redness, swelling or hardness. They should also ask subjects about itching, dizziness or shortness of breath. Patients should be advised that if they experience redness, swelling or other changes at the injection site, they should notify site personnel. They should further be advised that if they experience itching all over or a feeling of being swollen, dizzy or short of breath, they should notify site personnel or their own healthcare provider immediately.

Vital signs will be taken pre-dose, 5 minutes, and 1 hour (at roll-over visit) or 30 minutes (at following visits) after the dose is administered (cf. [Flow Chart](#)). Hypersensitivity reactions should be treated according to medical standards. Pre-medications for further injections might be considered and will be agreed on between investigator and BI clinical monitor.

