#### **Definition of Baseline**

1. Baseline is defined as the last non-missing value on or before the date of the first dose of study drug in Study 1311.2. The efficacy analyses will use these baseline values. These baseline values will be referred to as "BL" in this document.
2. RZB baseline is defined as the last non-missing value on or before the date of the first dose of risankizumab either in Study 1311.2 or this study. For vital sign assessments, only assessments prior to first dose time will be considered, since vital signs are to be assessed both pre- and post-dose in some visits. These values

will be referred to as BL\_RZB in this document. BL\_RZB will be used for safety analyses.

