### **Definition of Analysis Windows**

All time points and corresponding time windows are defined based on Rx Days.

For efficacy analyses, local tolerability, laboratory parameters, study drug injections, and vital sign variables, analysis windows are constructed using the following algorithm:

- Determine the nominal Rx day for each visit (e.g., Week 4 [4 weeks after Baseline visit] equals Rx Day 29).
- In order to include all post baseline data, the first post-baseline interval starts on the first day after the first dose of risakizumab (Rx Day 2).
- Determine the window around a specific nominal Rx day by adding or subtracting half of the interval between adjacent visits (e.g., days between Week 2 and Week 4 is 14). The threshold between adjacent visits is determined by splitting the interval evenly between the visits. If the resulting

split is between Rx days, then the threshold is determined as the midpoint between the adjacent visits. If the resulting split is on an Rx day, then the threshold is determined as being between that Rx day and the Rx day prior to it (e.g., the split between Week 2 and Week 4 would be between Rx Days 22 and 23).

- If more than one assessment is included in a time window the assessment closest to the nominal day will be used. If there are two observations equidistant to the nominal day, the one after the nominal day will be used in analyses. If more than one post baseline assessment is included on the same day, then the worst assessment on that day will be used in analyses, except those specified in Section 11.0.

The protocol specified visits and corresponding time windows used in the efficacy analyses, study drug injections, local tolerability, clinical laboratory tests, and vital sign variables, are presented in the following **Table 1**.

**Table 1. Visit Windows for Analysis of PASI, sPGA, Pain Vas, DLQI, Study Drug Injections, Local Tolerability Assessment, Clinical Laboratory Tests, and Vital Signs**

Window label	Target day	Interval
Entry of this study a	1	$\leq 1^b$
Week 12	85	[2, 127]
Week 24	169	[128, 211]
Week 36	253	[212, 295]
...	...	...
Week K	$K \times 7 + 1$	$[K \times 7 - 40, K \times 7 + 43]$

a. There is no local tolerability measurements at entry of this study (Extended Visit 1).

b. If time is collected in vital signs, restrict to records prior to the first dose of RZB.

Note: Rx Day calculated relative to first dose date of risakizumab in this study.

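### After the first dose, the SAP's same-day average blends one pre-dose and two post-dose vital signs, so visit summaries are not comparable with baseline, study entry or Extended EOS

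*SAP*

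**What the plan says.** **Schedule.** Footnote 8 of the protocol's Flow Chart gives three readings at the first extended visit: "Extended visit 1: Vital signs will be taken ~ 30 min pre-dose, 5 minutes, and 1 hour after the dose is administered". It gives three at later ones: "Following dosing visits: Vital signs will be taken ~ 30 min pre-dose, 5 minutes, and 1 hour after the dose is administered". The non-dosing visit has one: "Non-dosing visit (Extended EOS): Vital signs will be measured once per visit". Protocol 4.1.4 states the later post-dose time differently, as "1 hour (at roll-over visit) or 30 minutes (at following visits) after the dose is administered".

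**Baseline and entry.** The SAP's Definition of Baseline says "For vital sign assessments, only assessments prior to first dose time will be considered", and gives as its reason that some visits have readings on both sides of the dose. Note b to Table 1 in SAP 6.0 treats the entry window in the same way: "If time is collected in vital signs, restrict to records prior to the first dose of RZB". The next window opens on Rx Day 2.

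**Visit summaries.** SAP 11.4.2 says "Observed values at each scheduled visit in vital sign parameters will be summarized with the mean, standard deviation, median, minimum and maximum" and then "If there are multiple post-baseline measurements on the same day, average value will be used". The general same-day rule in SAP 6.0 takes the worst value but exempts Section 11.0, so the average governs here.

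**Threshold outputs.** The next paragraph of SAP 11.4.2 plans a listing and a count of patients with any value that meets the Table 6 criteria. Table 6 covers systolic pressure, diastolic pressure and pulse only.

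**The concern.** The SAP recognises that pre-dose and post-dose readings should not be mixed, and separates them at baseline and entry. It drops that separation for later visits. At a dosing visit after the first dose in this study, two of the three averaged readings are post-dose. The columns of the summary table therefore hold different quantities: a pre-dose value at baseline and entry, a three-reading average at later dosing visits, and a single reading at Extended EOS.

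Two things are at stake. A trend across visits could reflect the immediate effect of the injection visit rather than long-term exposure. And protocol 4.1.4 places the post-dose readings within its monitoring for hypersensitivity, while protocol 2.3 names hypotension as one sign of a systemic reaction. No planned output shows the change from pre-dose to post-dose on the same day.

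**Working it through.** The documents state no figure for this point, so there is none to reproduce. The number of readings comes from the Flow Chart and the averaging rule from SAP 11.4.2. All shifts, correlations and patient values below are assumptions.

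**1. Which visits are affected.** Rx Day 1 is the first dose in this study. If time is collected, the entry window keeps only pre-dose records. The Day 1 post-dose readings then fall in no window, because the next one starts on Day 2. They are left out, not averaged in. Averaging applies at dosing visits after that. For patients already dosed under the pre-extended schedule, Extended Visit 1 is itself one of those later visits. Table 1 as shown has only week windows, so a single Extended EOS reading can share a row with three-reading averages.

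**2. Effect on the visit value.** With pre-dose value P, the average is [P + (P + d5) + (P + dLate)]/3 = P + (d5 + dLate)/3.

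| Assumed d5 (mmHg) | Assumed dLate (mmHg) | Visit value minus pre-dose (mmHg) |
|---|---|---|
| 0 | 0 | 0 |
| -5 | 0 | -1.7 |
| -5 | -5 | -3.3 |
| -15 | 0 | -5.0 |
| -15 | -5 | -6.7 |
| -30 | 0 | -10.0 |
| -30 | -30 | -20.0 |
| +10 | +5 | +5.0 |

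A shift at 5 minutes only is cut to one third. An equal shift at both times is cut to two thirds. With no systematic shift the difference is zero.

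**3. Effect on spread.** If the three readings have equal variance and a common correlation rho, the SD of their mean is sqrt((1 + 2 rho)/3) times that of one reading. For rho = 0.5, 0.7 and 0.9 this gives 0.82, 0.89 and 0.97. So even with no shift, SDs at these visits are not like for like with baseline or Extended EOS. The minimum and maximum are also those of averages.

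**4. What Table 6 catches.** Take systolic readings of 125, 85 and 120. The mean is 330/3 = 110, but 85 is at or below the limit of 90. If baseline was at least 105, the fall is at least 20, so the patient is listed and counted on the plain reading of the text. Now take 150, 110 and 150. The mean is 410/3 = 136.7, and 110 is above 90. The same-day fall of 40 mmHg does not meet the low criterion and is not visible in the visit summary.

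**5. What Table 6 does not cover.** It has no criteria for respiratory rate or temperature. For those two, the averaged summary is the only planned tabulation.

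**The case against.** The strongest reply is that a clinically important reading is not lost. The Table 6 outputs work on any single value, and for flagged patients every recorded value of that parameter is listed. Clinically relevant changes in vital signs are recorded as adverse events (protocol 5.2.2.1). Hypersensitivity and anaphylactic reactions are searched for and tabulated (SAP Table 2). Vital signs are a further safety endpoint, not a primary one. SAP 11.4.2 plans no change-from-baseline summary for them, and the study has no tests.

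Most of this stands, and it rules out three stronger readings that a reader might infer:

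- **That averaging hides an extreme pressure such as 85 mmHg.** The wording of the Table 6 outputs does not support this. The averaging sentence does come just before that paragraph, so a clarifying line is worthwhile, but the plain reading is that it governs the visit summaries only.
- **That the visit means are biased.** The documents give no evidence of a systematic post-dose shift, and without one the difference is zero.
- **That every dosing visit is affected.** The first-dose visit is pre-dose only if time is collected.

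The reply does not explain why the SAP separates pre-dose readings at baseline and entry but not afterwards. It offers no same-day change and nothing for respiratory rate or temperature beyond the average. That the study is descriptive does not remove the point, because these summaries are the product.

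**Conclusion.** The point holds in a limited form. After the first dose in this study, the by-visit vital-sign summaries combine one pre-dose and two post-dose readings and are not comparable with baseline, entry or Extended EOS. Post-injection shifts appear at one third of their size (5 minutes only) or two thirds (equal at both times). Any bias in the means depends on a shift whose size and sign the documents do not give. First-dose post-dose readings enter no visit summary if time is collected. If it is not, the entry restriction lapses and the mixing can reach that visit too.

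The gap is widest for respiratory rate and temperature. For blood pressure and pulse, Table 6 is a real safeguard against extreme values, though it does not measure same-day change. The conclusion assumes that the three readings are taken as the Flow Chart schedules them and that Table 6 is applied to individual readings. The correction should be made, but no primary endpoint depends on it.

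**What to change.** 1. **Reconcile the later post-dose time first.** The Flow Chart gives 1 hour at all dosing visits. Protocol 4.1.4 gives 1 hour at roll-over and 30 minutes afterwards. A table by time point needs one agreed definition.
2. **In SAP 11.4.2, replace the same-day average** with the pre-dose reading for by-visit summaries, and use the single reading at Extended EOS.
3. **Add one table** of same-day change from pre-dose at 5 minutes and at the later time, for all vital-sign parameters measured at both, including the first-dose visit.
4. **As a clarification only,** state that Table 6 is applied to individual readings.

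The cost is SAP wording and one table, since the readings are already scheduled. One condition must be checked: the SAP speaks of time only if it is collected, so confirm that each reading carries a clock time or a planned time-point label.
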